3 PLANNED ANALYSES

3.1 Safety Monitoring

No independent Data Monitoring Committee will be used in this study.

3.2 Interim Analysis / Primary Analysis

No interim analysis will be performed.

3.3 Final Analysis

Planned analyses will be done when all subjects completed study and after database lock.

4 ANALYSIS POPULATIONS

4.1 Screened population

All subjects screened (i.e. who signed the informed consent).

4.2 Run-in population

All subjects who received at least one injection in the pre-randomisation run-in period (Part A).

For analyses and displays, subjects will be classified according to randomised treatment allocated in part A.

4.3 Randomised population

All subjects randomised in the double-blind period (Part B).

For analyses and displays, subjects will be classified according to randomised treatment allocated in part B.

4.4 Safety population

All subjects who received at least one dose of the study drug during the randomised double-blind period (Part B).

For analyses on the safety population, subjects will be classified according to treatment received. If there is any doubt whether a subject was treated or not, he/she will be assumed treated for the purposes of analysis.

4.5 Per Protocol (PP) Population

All subjects from the randomised population for whom no major protocol deviation occurred.

5 STATISTICAL METHODS/ANALYSES

The statistical analyses will be performed in accordance with ICH E9 guideline and guidelines presented in section 8.

The statistical analyses will be performed by the Biostatistics unit of BIOTRIAL BIOMETRICS in agreement with the sponsor.

5.1 General Considerations

All statistical analyses will be performed using the SAS® software version 9.4 or higher.

For Part A, only listings will be provided. For Part B, tables, figures and listings will be provided.

5.1.1 *Outputs Presentation*

5.1.1.1 *Tables Header*

Depending on the type of data, the summary tables will be presented as follows:

- For disposition, demographic data and baseline data description: by treatment group and overall,
- For efficacy and safety data: by treatment group and all Dysport.

5.1.1.2 *Presentation of Treatment Group*

For Part A, listings will be displayed using the following treatment group labels, in the order presented:

Long label	Short label
Lidocaine 2.5mg/injection site	Lidocaine
Placebo	Pbo

For Part B, Tables, Figures and Listings (TFLs) will be displayed using the following treatment group labels, in the order presented:

Long label	Short label
Placebo	Pbo
Dysport 2.5U/Injection site	Dysport 2.5U*
Dysport 10U/Injection site	Dysport 10U*
Dysport 20U/Injection site	Dysport 20U*

* Per injection site

When specified, tables will also be described by total dose received in the painful injection area and the total dose received in the painful area divided by the painful area.

5.1.1.3 *Presentation of Visits / Timepoints*

Summaries by visit will be presented using visit number as collected in the electronic Case Report Form (eCRF).

Visits in the TFLs will be presented as follows and in that order:

Part	Long Visit Name	Short Name
	Screening	Scr
Part A	Injection test 1 (Day -21 max)	Inj1
	Injection test 2 (Day -14 max)	Inj2
Part B	Baseline (Day -7 Day -1)	Bsl
	Day 1 Pre-dose	D1 Pre-dose
	Day 1 Post-dose	D1 Post-dose
	Day 2 Day 7	D2 D7
	Week 2	W2
	Week 4	W4
	Week 6	W6
	Week 8	W8
	Week 10	W10
	Week 12	W12
	Week 14	W14
	End of Study	EOS

5.1.2 *Descriptive Statistics*

All raw and derived variables will be listed and described using summary statistics. For categorical variables, summary statistics will be displayed using descriptive statistics by frequency count and percentages by category. The missing category will be presented if there is one missing category for at least one treatment group. Except otherwise specified, subjects with missing data will not be included in the calculation of percentages. For quantitative variables, summary statistics will be displayed using descriptive statistics by number of observations, mean, standard deviation (SD), first quartile, median, third quartile, minimum and maximum. Missing data will be displayed.

5.1.3 *Baseline value*

Unless otherwise specified, baseline is defined as the last non-missing measurement taken within 7 days prior to IMP administration (including unscheduled assessments).

For the spontaneous NRS score, baseline will be defined as the mean of all pre-dose data (from day -7 and including pre-dose on Day 1).

5.1.4 *Reference Start Date and Study Day*

Reference start date is defined as the day of IMP administration in Part B.

The day of IMP administration will be Day 1. Study day will be calculated as:

- The difference between the event date and the reference date plus one day, if the event is on or after the reference date.
- The difference between the event date and the reference date, if the date of event is prior to the reference date.

Study day will appear in any Part B listings where an assessment date or event date appears.

In case of partial or missing event date, study day will appear missing while any associated durations will be presented based on the imputations described in appendix A3.

5.2 Randomisation, Disposition and Population

A listing presenting randomisation details will be provided for Part A and Part B separately.

Following disposition summaries and listings will be provided:

- Summary table with the number and percentage of subjects screened, screen failed, reason for screen failures, randomised, completers, withdrawn and reason for withdrawal, by treatment group and overall,
- Summary table on duration of subject participation in the study, for Part B. The definition of the duration of subject participation is from the date of consent to the last study visit,
- Summary table with the number and percentage of non-responders' subjects at the end of Part A,
- Listing of subject disposition,
- Listing of dates of visit including duration of subject participation,
- Listing of screen failure subjects with the criteria not met,
- Listing of withdrawal subjects,

Following analysis population summaries and listings will be provided:

- Listing of all inclusion criteria,
- Listing of subjects violated inclusion criteria,
- Listing of all exclusion criteria,
- Listing of subjects fulfilled exclusion criteria,
- Summary of the number and percentage of subjects in each analysis population by treatment group and overall, based on all randomised subjects with reasons for exclusion from each analysis population,
- Summary of the number and percentage of subjects in the run-in population with reasons for exclusion from this population,
- Listing including flag for each analysis population and reason for exclusion from each population.

5.3 Protocol Deviations

An exhaustive list of major protocol deviations that may occur during the study and any action to be taken regarding exclusion of subjects will be defined in Protocol Deviation Plan. Major protocol deviations will be determined before unblinding of the study, finalized during the blind data review and documented in a separate document.

Number and percentage of subjects with protocol deviations by deviation category (see DV section of Standard SDTM+ user guide) will be summarized on all randomised subjects. Listings of major protocol deviations will also be provided on the randomised population for Part B and on the run-in population for Part A.

5.4 Demography and Other baseline characteristics

All demographic and baseline characteristics summaries will be provided for the randomised population. No statistical comparison between treatment groups will be performed.

Following summaries will be provided on:

- Demographic variables (refer to appendix A6 for EudraCT age categories),
- Other baseline characteristics (e.g. drug abuse tests, postmenopausal status, serology),
- Disease characteristics at day 1 pre-dose (e. g. longitudinal axis, total painful area and baseline values for spontaneous current pain NRS score),

Details of the surgery which caused the painful scar will be listed (Surgical procedure, indication and date of surgery).

Listings will also be provided for all the summaries listed above.

An additional listing with demographic variables for subjects non included in part B will also be provided.

5.5 Medical history, non-drug therapies, medications and surgical procedures

Medical and surgical history, non-drug therapies and surgical procedures will be coded using the latest version of MedDRA in effect within IPSEN at the time of database lock. Medications will be coded using the latest version of WHO-Drug dictionary in effect within IPSEN at the time of database lock.

Medication, non-drug therapies and surgical procedures start and stop dates will be compared to the date of the IMP administration (Part B) to allow classification as either Prior only, Prior and Concomitant, or Concomitant only:

Prior (P)	Start and stop dates prior to the date of IMP administration.
Prior and Concomitant (PC)	Start date before the date of IMP administration and stop date on or after the date of IMP administration.
Concomitant (C)	Start date on or after the date of IMP administration.

Summary tables on prior medications/non-drug therapies/surgical procedures will include “P” only, summary tables on concomitant medications/non-drug therapies/surgical procedures will include “C” and “PC”.

See detailed rules in appendix A3 for classification of prior and concomitant medication/non-drug therapies, surgical procedures in case of partial/missing date.

The therapeutic class will correspond to the second level of ATC code, that is, corresponding to the first 3 figures.

Following summaries, presenting count and percentages of subjects will be provided:

- Medical and surgical history by primary system organ class (SOC) and preferred term (PT),
- Prior medications (P) by ATC class and PN (ATC level 2),
- Concomitant medications (PC, C) by ATC class and PN (ATC level 2),
- Concomitant medications (PC, C) related to medical history by ATC class and PN (ATC level 2),
- Prior non-drug therapies (P) by primary SOC and PT,
- Concomitant non-drug therapies (PC, C) by primary SOC and PT,
- Concomitant surgical procedures (C) by primary SOC and PT,

A specific listing of medications from the class ANALGESICS, ANTIINFLAMMATORY AND ANTIRHEUMATIC PRODUCTS, ANTIPRURITICS, INCL. ANTIHISTAMINES, ANESTHETICS, ETC. and PSYCHOANALEPTICS (ATC level 2) and a specific listing of the concomitant medication related to medical history will be provided.

Listings will be provided for all the summaries listed above for Part B. These listings should include a flag indicating the category (P, PC, C) as described in the table above.

5.6 Compliance

Treatment compliance will be summarized on the run-in population for Part A and on the safety population for Part B using a listing of administrations and planned and performed injected volumes (overall and by injection site).

5.7 Pharmacodynamic/Efficacy Part B

5.7.1 General Considerations

5.7.1.1 Significance Testing and Estimations

The statistical analysis of efficacy and safety is only descriptive therefore no formal statistical significance testing will be performed.

5.7.1.2 Statistical/analytical issues

Adjustments for Covariates

Not applicable

Handling of Dropouts or Missing Data

The strategy for missing data handling is specified in each relevant section.

Interim Analyses and Data Monitoring

Please refer to section 3.

Multicentre Studies

Not applicable

Multiple Comparisons/Multiplicity

No formal statistical significance testing will be performed.

Use of an "Efficacy Subset" of Subjects

Not applicable

Active-Control Studies Intended to Show Equivalence (if applicable)

Not applicable

Examination of Subgroups

Subgroups analyses will be detailed in the concerned sections.

5.7.2 *Pre-randomisation run-in period*

A listing presenting NRS data will be provided. The listing will present, by subject, the planned visit and timepoint, the treatment administered, the assessment dates and the NRS scores.

5.7.3 *Randomised double-blind period: Analysis of Primary Efficacy Endpoint*

5.7.3.1 *Endpoint, Treatment Effect and Estimand Definition*

To assess the primary objective, the treatment policy estimand is defined by the following key attributes:

- Population: Subjects in the randomized population
- Assessment: Worst pain and average pain within the last 12 hours as assessed by the spontaneous NRS score
- Variables (Endpoints): Described in table below
- Population-level summary (estimate of the treatment effect): Described in table below

Variables (Endpoints)	Population-level summary (estimate of the treatment effect)
Time to onset i.e. time to decrease from baseline of two points in the spontaneous NRS score. Derivation: First scheduled time point for which the change from baseline is ≤ -2 points.	The number (%) of subjects who reach the time to onset in each treatment group. The mean time to onset in each treatment group
Peak effect i.e. maximal decrease from baseline in the spontaneous NRS score. Derivation: Minimum change from baseline amongst the scheduled timepoints	The mean peak in each treatment group
Time to peak-effect i.e. time to reach the peak-effect Derivation: First timepoint for which the peak effect is reached	The mean time to reach the peak-effect in each treatment group
Duration of effect (in days) i.e. duration between time to onset and last timepoint with decrease from baseline in the spontaneous NRS score is \geq two points Derivation: Duration is calculated as: last timepoints for which change from baseline ≤ -2 – time to onset (in days)	The mean duration of effect in each treatment group (for the subjects who reach the time to onset)

Each endpoint will be evaluated using the worst pain within the last 12 hours and using the averaged pain within the last 12 hours.

5.7.3.2 *Primary Analysis*

For each estimate, analysis will be based on the treatment policy estimand: No adjustment will be made in case of intake of rescue medication. No handling of missing data will be performed in the primary analysis.

Listings will be provided including all subjects with missing values for the 4 primary endpoints based on the NRS score. For subjects with missing values, the listings will provide all observed data related to the primary endpoints i.e. all measurements recorded prior to the missing value, any measurements recorded after the missing value, important baseline characteristics, the reason for study discontinuation and the timing of study discontinuation.

Summary table for time to onset, peak-effect, time to peak effect and duration of effect will be computed for each assessment, by treatment group and Placebo versus all Dysport groups.

The number and percentage of subjects who reach the time to onset will be presented for each assessment, by treatment group.

For each assessment, scatter plots and box whisker plots will be generated for the comparison of the peak effects between the treatment groups and all Dysport groups.

5.7.3.3 *Sensitivity Analysis*

The same analyses as described in section 5.7.3.2 will be performed on the PP population using the uncorrected parameters if important differences, i.e. at least 2 patients in the same treatment group, between the randomised population and the PP population are observed: the need for this analysis will be discussed during the blind data review meeting.

5.7.3.4 *Supplementary Analysis*

Not applicable.

5.7.3.5 *Subgroup Analysis*

No subgroup analyses will be performed.

5.7.4 *Randomised double-blind period: Analysis of Key Secondary Efficacy Endpoints*

5.7.4.1 *Endpoint, Treatment Effect and Estimand Definition*

To assess the secondary objectives, the treatment policy estimand is defined by the following key attributes:

- Population: Subjects in the randomised population
- Assessments: Described in table below
- Variables (Endpoints): Described in table below

- Population-level summary (estimate of the treatment effect): Described in table below

Assessment	Variables (Endpoints)
Spontaneous pain as assessed by the spontaneous NRS score	Change from baseline in the spontaneous NRS score to each scheduled timepoint
Stimulus evoked pain as assessed by the NRS score during QST	Change from baseline in the stimulus evoked NRS score to each scheduled timepoint

Spontaneous NRS Score

For each visit, spontaneous NRS (average and worst pain) score is assessed twice per day. The 2 assessments will be described separately as well as the daily average (mean of the NRS score assessed in the morning and in the evening) for the average NRS and the daily worst value for the worst NRS scores (worst NRS score assessed by day).

Baseline will be derived as defined in section 5.1.3.

To support the analyses of NRS score, the following endpoints will be considered:

- Time weighted Sum Pain Intensity Differences (SPID) from time 0 to each visit:

$SPID_{0-wx} = \sum_{i=0}^{i=n} CHG_i (t_{i+1} - t_i)$ where t_0 is the baseline time, t_i is the scheduled assessment time and CHG_i is the change from baseline in pain intensity at each post-dose scheduled timepoint.

- Sum Pain Intensity Differences Area Calculation (Area Under the Effect (AUE)):

$AUE_{0-wx} = \sum_{i=0}^{i=n} (CHG_i + CHG_{i+1})/2 * (t_{i+1} - t_i)$ where t_0 is the baseline, t_i is the scheduled assessment time and CHG_i is the change from baseline in pain intensity at each post-dose scheduled timepoint.

SPID and AUE will be evaluated at each visit (Week 6, Week 12 and end of study) using the worst pain within the last 12 hours and using the average pain within the last 12 hours, based on the spontaneous NRS score.

Painful Area Mapping

Painful area mapping includes longitudinal axis (cm) and total painful area (cm^2). It is assessed at screening, injection test 1 and 2, baseline, day 1 pre-dose, week 6, week 12 and end of study. Change from baseline will be derived for each parameter.

QST

The stimulus evoked NRS score is assessed during QST at baseline (day -7 day -1), week 6 and week 12, and include the following parameters:

- **Baseline assessment** on contralateral/non-painful area on painful area: NRS assessment is performed on each area (baseline assessments).

Change from baseline will also be derived at each timepoint for baseline assessment, for the painful area only.

- **Temporal summation** on painful area only: NRS score is recorded pre-stimulus and 10 attempts are performed after stimulus.
Change from baseline will also be derived at each time point as follows: NRS score from the last set of attempts – NRS pre-stimulation.
- **Tactile detection thresholds** on contralateral/non-painful area and on painful area: results (in g) will be assessed to determine sensory and pain perception threshold on each area.
Thresholds are assessed on a logarithmic scale. It will be converted to a linear scale for the analysis (see section 7).
Change from baseline will also be derived at each time point, for the painful area only.
- **Mechanical pain sensitivity and dynamic mechanical allodynia** on contralateral/non-painful area and on painful area: on each area, NRS-score will be assessed during static mechanical allodynia and dynamic mechanical allodynia.
Change from baseline will be derived at each time point, for the painful area only.
- **Pressure pain thresholds (PPT) (in kg/cm²)** on contralateral/non-painful area and on painful site: 3 readings of PPT, as well as their average, will be assessed in 4 positions, on each area. The global average of all the PPT values from all the positions will be derived for the painful and non-painful area.
Change from baseline on the global average PPT will also be derived for the painful area only.
- **Conditioned pain modulation (CPM)** on painful area will be performed and the following parameters will be determined:
 - a. 2 NRS scores: baseline and resulting NRS (cuff in situ).
 - b. Duration of cuff occlusion (in min:sec)
 - c. Clenching (Yes/No)
 - d. Pressure applied (in mmHg)
 - e. 3 PPT readings (in kg/cm²) and their average.CPM is assessed at the point on the painful area with the lowest PPT value from the previous test. A flag should be added if CPM is not evaluated at the lowest PPT position. Change from baseline on the average PPT for the painful area will also be derived.
- **Thermal detection and pain thresholds** on contralateral/non-painful area and on painful area including cold sensation (in °C; 4 replicates and the average), warm sensation (in °C; 4 replicates and the average), cold pain (in °C; 3 replicates and the average) and heat pain (in °C; 3 replicates and the average).
For each subject, the number of incorrect perception of temperature by test will be derived for the painful and non-painful area.

Temperatures below or equal to 0°C and temperatures above or equal to 50°C are not reliable for the analyses and therefore will be excluded from the statistical analyses.

5.7.4.2 *Main Secondary Analysis*

For each estimate, analysis will be based on the treatment policy estimand: No adjustment will be made in case of intake of rescue medication.

Painful Area Mapping

Summary table for raw data and changes from baseline of the longitudinal axis and the total painful area will be provided by treatment group and measurement time and Placebo versus all Dysport groups by measurement time.

Spontaneous NRS scores

Each analysis on the spontaneous NRS score will be produced separately for the Average Numeric Pain Rating and the Worst Numeric Pain Rating.

Summary table for raw data and changes from baseline in the spontaneous NRS score will be produced by treatment group, and measurement times, only for the daily average for the average NRS scores and for the daily worst for the worst NRS scores).

The graph of arithmetic mean \pm SD over time will be provided for the change from baseline in the spontaneous NRS score (daily average for the average NRS and the daily worst for the worst NRS) with all treatment groups on the same graph. Size groups at each time point will also be presented on the graph.

The graph of arithmetic mean \pm SD over time will be provided for the change from baseline for the morning score and evening score on the same graph, separately for each treatment group.

Individual raw data and change from baseline spontaneous NRS score versus time profiles will be presented graphically for each subject with the worst numeric pain rating within the last 12 hours and the average numeric pain rating within the last 12 hours on the same graph.

Listings of individual data of the spontaneous NRS scores will be provided including all subjects with missing data. Values measured on a day where a rescue medication was taken will be flagged.

Summary table for SPID and AUE parameters will be computed for each assessment, by treatment group and visit.

For each assessment, scatter plots and box whisker plots will be generated for the comparison of SPID and AUE between the treatment groups.

Listing of individuals values of SPID and AUE will be provided.

OST analyses

Baseline assessments

Summary tables for raw data and changes from baseline in the NRS score will be produced by treatment group and measurement times.

Scatter plots of individual values at each time point will be presented with the arithmetic means by time point, linked by treatment group. All treatment groups will be presented on the same graph.

Individual values-time profiles (spaghetti plots) will also be presented for each treatment group on linear scale.

For the baseline assessments, individual histograms of the raw values of the NRS score will be provided to compare non-painful area with the painful area, for each measurement times. Values at painful and non-painful areas will be presented on the same graph.

Tactile detection thresholds

For each test (sensory threshold and pain perception threshold), summary tables for raw data and changes from baseline will be produced by treatment group and measurement times.

For the painful area, scatter plots of Von Frey sensory threshold and pain perception threshold will be provided with arithmetic means linked between the visits for each group. All treatment groups will be presented on the same graph.

Individual values-time profiles (spaghetti plots) for each test will also be presented for each treatment group on linear scale.

For each test, individual histogram will be provided: for each subject, the Von Frey reference will be represented at each time point for the painful area and the non-painful area on the same graph. For each value, the associated force value will be presented on the graph.

Mechanical pain sensitivity and dynamic mechanical allodynia

For each test (static mechanical allodynia and dynamic mechanical allodynia), summary tables for raw data and changes from baseline in the stimulus-evoked NRS scores will be produced by treatment group and measurement times.

For each test, for the painful area, scatter plots of stimulus-evoked NRS scores will be provided with arithmetic means linked between the visits for each group. All treatment groups will be presented on the same graph.

Individual NRS score-time profiles (spaghetti plots) for each test will also be presented for each treatment group on linear scale.

For each test (static mechanical allodynia and dynamic mechanical allodynia), individual histogram will be provided: for each subject, the raw NRS data will be

represented at each time point for the painful area and the non-painful area on the same graph.

Temporal summation at painful area

Summary tables for the pre-stimulus NRS score and the 10 attempts post-stimulation will be provided for raw data by treatment group and measurement times. Summary tables will also be provided for change from baseline by treatment group and measurements.

The number of repetitions will also be described by treatment group and measurement times.

The graph of arithmetic means according to the stimulation set numbers will also be provided for each treatment group with all visits on the same graph. Treatment groups will be presented on separated graph.

Individual graphs of the NRS-score profile (pre-stimulus and post-stimulus) will also be provided, with all visits on the same graph: raw NRS score will be displayed (y-axis) according to the stimulation set number (x-axis). The Von Frey filaments used (von Frey Reference) will be indicated on each individual graph.

Pressure pain thresholds (PPT)

Summary tables of raw data and changes from baseline (only for the painful area) for the global average PPT will be produced by treatment group and measurement times.

For the painful area, scatter plots of the global average PPT will be provided with arithmetic means linked between the visits for each group. All treatment groups will be presented on the same graph.

Individual values-time profiles (spaghetti plots) for the global average PPT will also be presented for each treatment group on linear scale.

Individual histogram of the average pressure at each timepoint will be provided. Values for painful and non-painful area will be represented on the same graph.

Conditioned pain modulation

Average raw data and change from baseline will be described by treatment group and measurement times. Average PPT measured during previous test, at the same position as the CPM will also be described in this table.

Box-whisker plots will be generated for the comparison of CPM and PPT between treatment groups.

Individual histogram of the average PPT measured during CPM on the painful area and the average PPT measured during the previous test, at the same position on the painful area at each timepoint will be provided. Footnote will be added if CPM is

not evaluated at the lowest PPT position. Position chosen will be reported for each time point.

Thermal detection and pain thresholds

For each test (cold sensation, warm sensation, cold pain and warm pain), average raw data will be described by treatment group and measurement times.

For each test, summary tables of the correctness of the answers will also be provided by treatment group and measurement times.

For each test, for the painful area, scatter plots of the average sensation temperature will be provided with arithmetic means linked between the visits for each group. All treatment groups will be presented on the same graph.

Summary table with the number of subjects with not done assessments will be provided with the reason for not done, by treatment group and measurement times. Subjects with excluded values (values ≤ 0 and values ≥ 50) will be included in this table with the reason 'Values excluded from analyses as threshold exceeded'.

Individual average sensation temperature-time profiles (spaghetti plots) for each test will also be presented for each treatment group on linear scale.

For each test, individual histogram of the average temperature for the change sensation will be provided at each time point. Values at painful and non-painful area will be presented on the same graph.

A listing of the number of incorrect perception of temperature will be provided.

All categories for QST

Listings of individual assessments performed during QST will be provided by category of QST.

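### Mean time to onset and mean duration rest only on subjects who reach a 2-point drop, and the SAP has no censoring rule for those who never reach it or leave first

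*SAP*

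**What the plan says.** SAP 5.7.3.1 sets the primary estimand for all randomised subjects: "Population: Subjects in the randomized population". Time to onset is derived as "First scheduled time point for which the change from baseline is ≤ -2 points". It has two summaries by arm: "The number (%) of subjects who reach the time to onset in each treatment group", then "The mean time to onset in each treatment group". Duration has one: "The mean duration of effect in each treatment group (for the subjects who reach the time to onset"). Table 3 in protocol 11.3.3.2 sets the same summaries.

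SAP 5.7.3.2 adds "No handling of missing data will be performed in the primary analysis", and plans the proportion again for both worst and average pain: "The number and percentage of subjects who reach the time to onset will be presented for each assessment, by treatment group". Subjects with missing primary endpoint values are to be listed with their observed scores and the reason for and timing of discontinuation.

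SAP 5.1.2 lists the statistics for quantitative variables: n, mean, SD, quartiles, median, minimum and maximum. For categorical variables its default is "Except otherwise specified, subjects with missing data will not be included in the calculation of percentages". Nothing in the SAP gives a censoring rule, a Kaplan-Meier estimate or a restricted mean for time to onset.

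Protocol 11.3.3.2 promised sensitivity analyses to handle missing data. SAP 2.6 withdraws them, subject to confirmation at the blind data review. What remains is a conditional repeat of the same summaries on the per-protocol population (SAP 5.7.3.3).

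**The concern.** Time to onset is a time-to-event variable, but it is summarised as an ordinary measurement. Two kinds of subject have no value: those followed for 16 weeks without a 2-point drop, and those who leave before one. The plan distinguishes neither from the other nor from a technically missing score. Early leavers are foreseen, since both documents provide for replacing subjects who withdraw in the first six weeks, and a replaced subject stays in the randomised population.

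The SAP does not say that the onset mean is over reachers only. That follows from the derivation together with the absence of any missing-data rule. For duration the restriction is written out.

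Describing onset and duration is the primary objective, so these summaries are the main result. A mean over reachers answers how fast onset was in those who had it. It does not answer how onset is distributed among the subjects randomised to a dose, which is the population that the SAP names.

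**Working it through.** **Arm size.** Both documents give a 3:1:3:1:3:1 ratio in blocks of 12. Two blocks give 2 × 3 = 6 subjects on each Dysport dose and 2 × (1 + 1 + 1) = 6 on placebo, total 24. This reproduces the stated 24. Follow-up is 16 weeks, T = 112 days (protocol 3.1).

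**Assumptions.** The documents give no reaching rate, onset time or SD. All rates and times below are illustrative, with complete follow-up.

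**1. Same course in reachers, different numbers reaching.** Suppose every reacher has onset at day 14 and duration 56 days, and k of 6 reach. The reachers-only means are 14 and 56 days for any k ≥ 1. Counting never-reachers at 112 days for onset and 0 for duration gives (14k + 112(6 − k))/6 and 56k/6.

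| k of 6 | Reachers-only onset, duration (days) | All-subject onset, duration (days) |
|---|---|---|
| 1 (16.7%) | 14, 56 | 95.7, 9.3 |
| 5 (83.3%) | 14, 56 | 30.3, 46.7 |

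The two means do not separate these arms. The planned number (%) does.

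**2. Exponential onset, 30% and 80% reaching by day 112.** With rate L = −ln(1 − p)/T:
- Mean among reachers = 1/L − T(1 − p)/p.
- Restricted mean over all subjects = p/L.
- p = 0.3: 1/L = 314.0. Reachers 314.0 − 261.3 = 52.7 days; all subjects 0.3 × 314.0 = 94.2 days.
- p = 0.8: 1/L = 69.6. Reachers 69.6 − 28.0 = 41.6 days; all subjects 0.8 × 69.6 = 55.7 days.

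The gap is about 11 days among reachers and about 38.5 days over all subjects.

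**3. How many subjects carry the mean.** With p = 0.3 and n = 6:
- P(0 reach) = 0.7⁶ = 0.118.
- P(1 reaches) = 6 × 0.3 × 0.7⁵ = 0.303.
- P(2 reach) = 15 × 0.3² × 0.7⁴ = 0.324.

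So P(2 or fewer) = 0.74. In about 12% of trials this arm has no mean at all.

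**4. Reading the mean alone and with the proportion.** Under the rates in step 2, both arms have at least one reacher in 88% of simulated trials. Among those:
- The arm with the lower reaching rate has the shorter reachers-only mean in about 36%, against about 4% for the all-subject restricted mean.
- In about 94.6% of the reversed trials, the number (%) reaching still favours the better arm.
- Both point the wrong way, or the proportions tie, in about 0.36 × (1 − 0.946) = 1.9%.

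**5. Chance dips.** Daily scores were simulated with within-subject SD 0.5 to 1.5 and day-to-day correlation 0.3 or 0.8. In the effective arm, 70% of subjects had a 3-point effect. By noise alone, 7% to 97% of a no-effect arm reached onset. Reachers-only onset averaged 15 to 50 days without effect and 8 to 14 days with it; duration averaged 14 to 83 and 70 to 92 days. The arms came closest at SD 1.5 and correlation 0.3 (15 against 8 days; 83 against 92 days), but were not equal on average in any setting.

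**The case against.** The strongest reply is that the plan already gives a two-part description: the proportion reaching onset, then the mean among those who did. The proportion is the summary named before the mean and is planned by arm for both pain scores. The same count tells the reader how many subjects stand behind the duration mean. SAP 5.1.2 prints n with each mean, subjects with missing values are listed, and peak effect does not condition on onset. The study is descriptive, with no tests. Comparison with placebo is a secondary objective, served by change from baseline.

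Most of this stands, and it rules out three stronger readings that a reader might infer:
- That non-responders disappear from these endpoints. They are counted in the number (%) reaching onset.
- That an ineffective arm should be expected to look as fast and as long-lasting as an effective one. In steps 2 and 5 the better arm keeps the faster average onset. Reversal is small-sample variation, and the 36% applies to someone who reads the mean and ignores the proportion.
- That duration must be set to 0 for never-reachers. This merges how many respond with how long the effect lasts in those who do, and the SAP openly labels its restriction.

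What remains is that a proportion beside a mean does not change what the mean estimates. The proportion also treats a subject who leaves at week 3 without onset either as a 16-week failure or as missing. The SAP does not say which, and its default on percentages leaves the denominator open.

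**Conclusion.** The point holds as a gap in specification and a weak choice of summary. It should be fixed, but it is not a fatal flaw. The mean time to onset is over reachers by derivation, and the mean duration is so by explicit wording. Neither describes the randomised population that SAP 5.7.3.1 names, and early leavers have no defined place in the onset summary.

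The size depends on the reaching rates, which the documents do not give. At 30% and 80%, restricting to reachers shrinks an all-subject difference of about 38 days to about 11, and the weaker arm's mean rests on two or fewer subjects in about three trials in four. Read with the planned proportion, the table would seldom mislead about which arm did better. It would still misstate how long onset takes in the arm as a whole.

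**What to change.** In SAP 5.7.3.1 and 5.7.3.2:

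1. Summarise time to onset by Kaplan-Meier, by arm, for all randomised, dosed subjects. Dosing is the time origin, so an undosed subject contributes no follow-up. Censor at the last NRS score if onset has not been reached. Give the median, or state that it was not reached, and the cumulative % with onset at Weeks 2, 6, 12 and 16.
2. Keep the mean onset and mean duration, labelled as reachers-only, and print the number (%) reaching onset beside both.
3. State that the denominator of that percentage is all randomised, dosed subjects.
4. Optionally add duration with 0 days for never-reachers as a supplementary line. It should not replace the labelled mean.

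The cost is SAP wording and two table shells, with no new data. One limit should be accepted in advance: with six per arm and complete follow-up, the median needs at least three reachers. An arm with a 30% reaching rate would show it as not reached in about 74% of trials. There the cumulative percentages carry the information, and the gain over the planned number (%) lies mainly in timing and in the treatment of early leavers.
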